11.5. Appendix 5: Data Display Standards & Handling Conventions

11.5.1. Reporting Process

Software	

 The currently supported versions of SAS software will be used. 	
Reporting Area	
HARP Server	: UK1SALX00175
HARP Compound	: /arenv/arprod/gw685698/hza114971
Analysis Datasets	

 Analysis datasets will be created according to current CDISC standards (Study Data Tabulation Model (SDTM) Implementation Guide Version 3.2 or higher & Analysis Data Model (AdAM) Implementation Guide Version 1.3 or higher). The same version of dictionary datasets will be implemented for conversion from SI to SDTM in the creation of ADaM datasets (ADCM/ADAE). 	
Generation of RTF Files	

 RTF files will be generated for Table displays to support the Clinical Study Report (CSR) development. 	

11.5.2. Reporting Standards

General

 The current GSK Statistical Display Standards in the GSK Standards Library (IDSL) will be applied for reporting, unless otherwise stated (Library Location): https://spope.gsk.com/sites/IDSLLibrary/SitePages/Home.aspx 
 4.03 to 4.23: General Principles 5.01 to 5.08: Principles Related to Data Listings 6.01 to 6.11: Principles Related to Summary Tables 7.01 to 7.13: Principles Related to Graphics Do not include participant level listings in the main body of the GSK Clinical Study Report. All participant level listings should be located in the modular appendices as ICH or non-ICH listings Note: All data displays (Tables, Figures & Listings) produced as part of the Statistical Analysis Complete (SAC), will use the term "Subject" which reflects GSK Data Display Standards terminology.
Formats

 Unless otherwise stated, all results will be reported according to the treatment to which the participant was randomised. GSK Statistical Display Principles (5.03 & 6.06.3) for decimal places (DP's) will be adopted for reporting of data based on the raw data collected, unless otherwise stated. Numeric data will be reported at the precision collected on the eCRF or recorded in the raw dataset if from non-eCRF sources. The reported precision from non eCRF sources will follow the GSK Standard Statistical Display Principles but may be adjusted to a clinically interpretable number of DP's. Summary and analysis data displays will include the following degrees of precision:

Specification of Number of Decimal Places for Descriptive Statistics		
Label	Description	No. of decimal places more than raw data
N	Number of participants in the treatment group	0
n	Number of participants with non-missing values	0
Mean	Arithmetic mean	1
SD	Standard deviation	2
Median	Median	1
Min.	Minimum	0
Max.	Maximum	0
Specification of Number of Decimal Places for Statistical Analyses		
Label	Description	No. of decimal places more than raw data
LS Mean	Least squares adjusted mean for the treatment group	1
Std Err	Standard error	2
Difference	Treatment difference	1
95% CI	95% Confidence interval around treatment difference/ratio	Same as difference or ratio
Planned and Actual Time		

 Reporting for tables, figures and formal statistical analyses: 
 Planned time relative to dosing will be used in figures, summaries, statistical analyses and calculation of any derived parameters, unless otherwise stated. The impact of any major deviation from the planned assessment times and/or scheduled visit days on the analyses and interpretation of the results will be assessed as appropriate. Reporting for Data Listings: 
 Planned and actual time relative to study drug dosing will be shown in listings (Refer to GSK Standard Statistical Display Principle 5.05.1). Unscheduled or unplanned readings will be presented within the participant's listings. 		
Unscheduled Visits		

 Height data collected at unscheduled visits will be included in summary tables, analyses and/or figures, unless otherwise specified. Unscheduled visits will be clearly labelled as unscheduled and slotted based on date of visit. All unscheduled visits will be included in listings. 		
Descriptive Summary Statistics		
Continuous Data	Refer to GSK Standard Statistical Display Principle 6.06.1	
Categorical Data	N, n, frequency, %	
Graphical Displays		

 Refer to GSK Standard Statistical Display Principals 7.01 to 7.13. The programs for statistical analysis tables will create SAS datasets with the unrounded numbers from the statistical models to be used in any graphs. These datasets will include all LS means, standard errors, treatment differences or ratios, and CIs. These analysis datasets will be created for all analysis tables regardless of whether or not a figure is planned as part of SAC. 		

- The programs for all graphical displays will also create a CSV file with the final data that is used in the graph in order to allow the graph to be redrawn for any potential publication requirement in the future.

11.6. Appendix 6: Derived and Transformed Data

11.6.1. General

Multiple Measurements at One Analysis Time Point

 If a circumstance should arise where multiple measurements have been collected and recorded against the same time point, then the first valid value will be used for that time point. If the value that was recorded first cannot be determined based on the available information, then the average will be taken.
Study Day

 Calculated as the number of days from Randomisation Date: 
 Ref Date = Missing → Study Day = Missing Ref Date < Randomisation Date → Study Day = Ref Date – Randomisation Date Ref Date ≥ Randomisation Date → Study Day = Ref Date – (Randomisation Date) + 1
Time Since First Dose

 Calculated as the number of days from First Dose Date of Double-Blind Treatment: 
 Ref Date = Missing → Time Since First Dose = Missing Ref Date < First Dose Date → Time Since First Dose = Ref Date – First Dose Date Ref Date ≥ First Dose Date → Time Since First Dose = Ref Date – (First Dose Date) + 1
Double-Blind Treatment Start/Stop Date

 Participants who permanently discontinue double-blind study treatment are encouraged to continue in the study, attend the remaining visits and complete the scheduled assessments. Data displays will state if on-treatment, off-treatment (as defined in Section 11.4.1), or both on-treatment and off-treatment data are included in the summary or analysis, when applicable. Double-Blind Treatment Start Date will be defined as the earliest treatment start date of double-blind treatment and Double-Blind Treatment Stop Date will be defined as the latest treatment stop date of double-blind treatment (from the study treatment compliance eCRF log and treatment discontinuation eCRF page). These dates will be used to determine whether a measurement is on-treatment or off-treatment (See Section 11.4.1).

11.6.2. Study Population

Demographics
Age

 • Age is being calculated in the Interactive Voice Recognition System (IVRS) and will be imported from the IVRS into the clinical database. • The IVRS will use GSK standard IDSL algorithms to calculate age. In accordance with GSK policy, only month and year are collected in the IVRS. A complete birthdate will be imputed by using the month and year recorded by the IVRS and assigning a day value of '15.' Any participant with a missing month will have day and month imputed as '30 June'. • Birth date will be presented in listings as 'YYYY'. • Completely missing dates of birth will remain as missing, with no imputation applied. Consequently, the age of the participant will not be calculated and will remain missing. • Age, in whole years, will be calculated with respect to the date of screening (Visit 1).
Body Mass Index (BMI)

 • Calculated as weight (kg) / height (m)².
Race

The high-level Food and Drug Administration (FDA) race categories and designated Asian subcategories are:
 
 1. American Indian or Alaska Native 2. Asian 
 a. Central/South Asian Heritage b. Japanese Heritage/East Asian Heritage/South East Asian Heritage c. Mixed Asian Heritage (only required if data exist) 3. Black or African Heritage 4. Native Hawaiian or other Pacific Islander 5. White 
These will be summarized along with all combinations of high-level categories which exist in the data. All high-level race categories and the Asian subcategories must appear on the display even if there are no participants in a particular category, but combinations that do not exist in the data do not need to be represented. Combinations will be represented as the concatenation of the high-level category terms, e.g., "White & Asian". The designated Asian subcategories will not be summarized as combinations with other categories.
 
In addition, the standard race categories collected per IDSL will be summarized along with categories for mixed race. The categories are:
 
 • American Indian or Alaska Native • Asian - Central/South Asian Heritage • Asian – East Asian Heritage • Asian – Japanese Heritage • Asian – South East Asian Heritage

- Native Hawaiian or other Pacific Islander
- White – Arabic/North African Heritage
- White – White/Caucasian/European Heritage
- Mixed White Race
- Mixed Asian Race
- Multiple

“Mixed Asian Race” is only used if more than one Asian category is selected, but no non-Asian races. Similarly, “Mixed White Race” is only used if both of the White categories are selected, and no non-White races. If multiple races of different types are selected, then the overall “Mixed Race” category is used. If multiple races of different types are selected, then the overall “Multiple” category is used.

A participant will only be represented in a single category. A participant who selects a combination of races will be counted as “Mixed Asian Race,” “Mixed White Race,” or “Multiple” but not in each of the constituent terms. Therefore, the counts will add up to the total number of participants with a response, and the percentages will add to 100%.

Treatment Compliance

Compliance with the study medication will be assessed throughout the study.

- Compliance with open-label montelukast will be assessed based on the daily eDiary data during both the run-in and double-blind treatment periods. The percentage of times the parent answered “Yes” to the question “Did your child take their daily Study Asthma Tablet yesterday evening?” will be summarized for each study period.
- Compliance with the single-blind/double-blind study inhaler will be assessed during the run-in/double-blind treatment periods based on the daily eDiary data. The percentage of times the parent answered “Yes” to the question “Did your child take their daily Study Medication Inhaler yesterday morning?” will be summarized for each study period.
- In addition, compliance with the single-blind/double-blind study inhaler during the run-in/double-blind treatment period will also be calculated based on the dose counter of the inhalers, which are re-supplied during the study. The number of doses of study inhaler taken by each participant will be calculated from the dose counter start and stop counts for each inhaler dispensed during the study. If a dose counter start count is missing, then it will be assumed to be 30. If dose counter stop count is non-missing, then the percentage compliance will be calculated as:

$$Compliance = \left(\frac{Total\ Number\ of\ Inhalations\ Taken}{Expected\ Inhalations \times (Stop\ Date - Start\ Date + 1)} \right)$$

where *Total Number of Inhalations Taken* is the total number of doses taken from all inhalers, *Expected Inhalations* is equal to 1 and *Start Date* and *Stop Date* are the earliest treatment start date and the latest treatment stop date recorded for all of the inhalers used in the calculation.

Participants who are either under- (<80%) or over- (>120%) compliant over the run-in and double-blind treatment periods according to both the diary card and the inhaler dose counter, will be identified. The numbers of these participants, as well as the number of participants whose compliance is unknown, will be summarized by treatment.

Extent of Exposure
 
 • Duration of exposure (days) to double-blind study treatment will be calculated as: 
 ○ Double-Blind Treatment Stop Date – Double-Blind Treatment Start Date + 1 • Participants who were randomised but did not report a double-blind treatment start/stop date, will have missing exposure. • Duration of post-treatment time (days) spent in the study will be calculated as: 
 ○ Study Conclusion Date – Double-Blind Treatment Stop Date • Duration of total time (days) spent in the study since first dose will be calculated as: 
 ○ Study Conclusion Date – Double-Blind Treatment Start Date + 1 • Double-blind treatment start and stop dates used will be the earliest (start) and latest (stop) of all dates recorded for the participant. Study conclusion is defined as completion or withdrawal, as applicable.

Concomitant Medications
 
 • Concomitant medications will be coded using the GSK Drug coding dictionary. Summaries of the number and percentage of participants taking concomitant medications will be displayed by ingredient without regard to Anatomical Therapeutic Chemical (ATC) classifications. These summaries will include single-ingredient medications and will present multi-ingredient medications according to the combination of the component ingredients. Summaries will be split into asthma and non-asthma concomitant medications, as well as into those taken pre-, on-, and post-treatment (as described in Section 11.4.1).

Screening Failures, Run-in Failures, Treatment Discontinuation, and Study Withdrawal
 
 • A participant who completes the screening visit and is dispensed single-blind study medication and electronic/paper diaries is considered to have entered the run-in period. Participants who enter the run-in period but are not randomised are considered run-in failures. • Participants who complete the run-in period but fail to meet all randomisation criteria are also considered to be run-in failures. • Participants who discontinue study treatment will not be automatically withdrawn from the study but will be encouraged to stay in the study. An Early Treatment Discontinuation Visit should be conducted within approximately 24 hours of the participant stopping study medication (or in the event a participant discontinues study treatment at or during a scheduled visit, all study procedures scheduled at an Early Treatment Discontinuation visit will be performed at this visit instead). These participants will not be allowed to restart study treatment; however, participants will be asked to continue to follow the regular visit schedule. • A participant will be considered discontinued from study treatment (i.e. double-blind treatment) if the participant was randomised, and has completed all visits including the follow-up visits, but prematurely discontinued from double-blind treatment during the treatment period. • The date of study treatment discontinuation refers to the date that a participant's study medication is intentionally and permanently stopped (as recorded in the eCRF).

Time to Study Withdrawal / Treatment Discontinuation
 
For Kaplan-Meier plots of study withdrawal over time and premature discontinuation from double-blind treatment over time, censoring will be performed as follows:
 
 • For study withdrawal, participants are represented from the date of start of double-blind treatment to the date of early withdrawal from the study (or date of death). Participants that completed the study are censored at the earliest of the date of completion or Day 423. • For premature discontinuation from study treatment, participants are represented from the date of start of double-blind treatment to the date of discontinuation from double-blind treatment (or date of death). Participants that complete study randomised treatment are censored at the earliest of their double-blind treatment stop date or Day 367.

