7.1.4. Strategy for Intercurrent (Post-Randomisation) Events

The primary treatment effect to be estimated is the treatment policy effect of initial randomised treatment. The list of intercurrent events/events leading to missing data that may occur during the study and may affect the estimation of the treatment effect are:

- **Discontinuation of Randomised Treatment:** Participants may prematurely discontinue double-blind treatment and continue in the study. This is considered an intercurrent event.
- **Participants Presenting Tanner Stage ≥ 2 :** Participants must be pre-pubertal (Tanner Stage 1) at the time of randomisation but may present physical characteristics of Tanner Stage 2 or higher at any point during the study. This is considered an intercurrent event.
- **Use of Rescue Systemic Corticosteroids:** Participants may receive rescue systemic corticosteroids at any point during the study. This is considered an intercurrent event.
- **Use of Rescue Inhaled/Intranasal Corticosteroids:** Participants may receive rescue inhaled/ intranasal corticosteroids at any point during the study. This is considered an intercurrent event.
- **Early Withdrawal from Study:** Participants may prematurely withdraw from the study which results in missing endpoint data.
- **Week 52 Height Not Available (other reasons than early withdrawal):** Height information at Week 52 may not be available for other reasons (not Early Withdrawal).

All available data up to the time of study withdrawal will be included in the primary analyses, regardless of discontinuation of randomised treatment, use of rescue corticosteroids, or Tanner Stage. To minimize study withdrawals, participants who

discontinue randomised treatment will be encouraged to stay in the study and complete all remaining protocol-specified visits and be followed-up as per the protocol until the completion of follow-up assessments. All non-missing data will be included in the primary analyses. Missing data will be assumed missing at random (MAR) in the primary analysis and will not be imputed. Missing data will be imputed in sensitivity analyses as described below in Section 7.1.6.

The strategies for handling these events for this endpoint are described in the below Table.

Event	Handling Strategy
Discontinuation of Randomised Treatment	Available height data will be used in the analysis, regardless of early discontinuation of randomised treatment.

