11.9.4. Study Population Tables

Study Population Tables					
No.	Population	GSK Standard / Example Shell	Title	Programming Notes	Deliverable [Priority]
Subject Disposition					
1.1.	Total	SP1	Summary of Study Populations	Only treatment arms and Total column to be presented.	SAC
1.2.	Total	ES6	Summary of Screening Status and Reasons for Screen Failure		SAC
1.3.	Total	IE1	Summary of Inclusion/Exclusion Criteria Deviations for Screen Failures		SAC
1.4.	Total	ES6	Summary of Randomisation Status and Reasons for Run-In Failure	This should present both randomised subjects and subjects classified as run-in failures.	SAC
1.5.	Total	IE1	Summary of Inclusion/Exclusion Criteria Deviations for Run-in Failures	This will include all run-in failures, including randomisation failures	SAC
1.6.	Total	NS1	Summary of Number of Subjects Enrolled by Country and Site ID -Total Population	EudraCT/Clinical Operations	SAC
1.7.	ITT	NS1	Summary of Number of Subjects Enrolled by Country and Site ID – Intent-to-Treat	EudraCT/Clinical Operations	SAC
1.8.	Total	Non-Standard POP_T1	Summary of Subjects Screened by Age		SAC
1.9.	ITT	ES1	Summary of Subject Status and Reason for Study Withdrawal	ICH E3, FDAAA, EudraCT	SAC

Study Population Tables					
No.	Population	GSK Standard / Example Shell	Title	Programming Notes	Deliverable [Priority]
1.10.	ITT	SD1	Summary of Study Treatment Status and Reason for Discontinuation of Study Treatment	ICH E3	SAC
1.11.	ITT	SD1	Summary of Treatment Status and Reasons for Discontinuation of Study Treatment by Relationship to COVID-19 Pandemic	Repeat of the existing table (that is based on SD1) but summarized by both "Related to COVID-19" and "Not-related to COVID-19"	SAC
1.12.	ITT	ES1	Summary of Subject Status and Study Disposition by Relationship to COVID-19 Pandemic	Repeat of the existing table (that is based on ES1) but summarized by both "Related to COVID-19" and "Not-related to COVID-19"	SAC
1.13.	ITT	Non-Standard POP_T2	Summary of Attendance at Each Visit		SAC
Protocol Deviation					
1.14.	ITT	Non-Standard POP_T3	Summary of Inclusion/Exclusion and Randomisation Criteria Deviations		SAC
1.15.	ITT	DV1	Summary of Important Protocol Deviations		SAC
1.16.	ITT	DV1	Summary of Important Protocol Deviations by Relationship to COVID-19 Pandemic	Repeat of the existing table (that is based on DV1) but summarized by both "Important Related to COVID-19" and "Important Not-related to COVID-19"	SAC
Demographic and Baseline Characteristics					

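### The SAP's definition of treatment discontinuation requires completion of all visits, so children who stop treatment and later leave the study would be missed in Tables 1.10 and 1.11

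*SAP*

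**What the plan says.** The definition is in SAP 11.6.2, in the block on screening failures, run-in failures, treatment discontinuation and study withdrawal. It covers randomised participants and adds two further conditions, that the child "has completed all visits including the follow-up visits, but prematurely discontinued from double-blind treatment during the treatment period". It is the SAP's only definition of this category.

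Other parts of the plan use treatment discontinuation without a visit-completion condition:

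- The next bullet of the same block dates discontinuation by the intentional, permanent stop of medication recorded in the eCRF.
- The Kaplan-Meier rule in SAP 11.6.2 says that "participants are represented from the date of start of double-blind treatment to the date of discontinuation from double-blind treatment", or to death. Only those who complete randomised treatment are censored.
- SAP 11.6.1 takes treatment start and stop dates from the eCRF and adds: "These dates will be used to determine whether a measurement is on-treatment or off-treatment".
- SAP 7.1.4 describes the intercurrent event as follows: "Participants may prematurely discontinue double-blind treatment and continue in the study. This is considered an intercurrent event".

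The counts and reasons are reported in Table 1.10, "Summary of Study Treatment Status and Reason for Discontinuation of Study Treatment", and again by relationship to COVID-19 in Table 1.11. Both use the ITT population. The list of displays in SAP 11.9.4 gives neither table a definition of its own.

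Protocol 5.5.1 treats stopping treatment and leaving the study as separate events and allows a child to do both.

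**The concern.** Stopping treatment is one event and finishing the study is another. A definition that joins them describes study completers who came off treatment, not everyone who came off treatment. A child who stops at Week 20 and withdraws consent at Week 30 fails it. So does a child who stops, attends Week 52 and misses a follow-up visit.

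What is at stake is disposition reporting. The primary effect is a treatment-policy effect, and a reader needs to know how many children in each arm stopped treatment, and why, to interpret it. Table 1.9 (study withdrawal) cannot fill the gap. Protocol 5.5.1 allows only two reasons for leaving the study: withdrawal of consent and loss to follow-up. If a child stops for non-compliance and later withdraws consent, the first reason is the one Table 1.10 exists to show, and the literal definition removes that child from it.

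**Working it through.** The plan states no figure for this point, so there is none to reproduce. The check compares the rules and adds one illustration.

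**Step 1. Conditions in the definition (SAP 11.6.2).** Three conditions are joined: (a) randomised, (b) all visits completed including follow-up, (c) double-blind treatment stopped early.

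**Step 2. Apply the rules to three children who stop treatment early.**

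| Child | Definition, SAP 11.6.2 | Kaplan-Meier rule, SAP 11.6.2 | Intercurrent event, SAP 7.1.4 |
|---|---|---|---|
| Stops Week 20, completes all visits | counted | event at stop date | meets wording |
| Stops Week 20, withdraws Week 30 | fails (b) | event at stop date | meets wording: stopped and continued for a time |
| Stops Week 20, attends Week 52, misses a follow-up visit | fails (b) | event at stop date | meets wording |

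Rows 2 and 3 are the inconsistency. The plot has an event for children whom the definition leaves out, although plot and table use the same ITT population.

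**Step 3. Illustration of size.** Let D be the number who stop early and w the share of them who later leave the study. The number counted under the literal definition is D × (1 − w).

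- D: Protocol 9.2.1 plans for up to 10% withdrawing from study medication in the first 12 weeks, and at least 450 randomised. 450 × 0.10 = 45. This is a planning ceiling for 12 weeks, used here only as a convenient number.
- w: not in the documents, so assumed.

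| w (assumed) | Counted | Missed |
|---|---|---|
| 0% | 45 × 1.00 = 45 | 0 |
| 25% | 45 × 0.75 = 33.75 (about 34) | 11.25 |
| 50% | 45 × 0.50 = 22.5 | 22.5 |
| 75% | 45 × 0.25 = 11.25 (about 11) | 33.75 |
| 100% | 45 × 0 = 0 | 45 |

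**Step 4. Does any growth estimate use the definition?** No. The primary analysis uses all available heights regardless of treatment discontinuation (SAP 7.1.4, 7.1.5.1). The on-treatment analyses select heights by treatment dates (SAP 11.4.1.1, 11.6.1).

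**The case against.** The strongest reply is that the sentence says if, not only if, and that the neighbouring bullet and the Kaplan-Meier rule show what was meant. The disputed bullet may have been intended to describe the subgroup who stopped treatment but finished the study. The link to Tables 1.10 and 1.11 is also inferred. They follow a sponsor standard shell that the documents do not reproduce, and the stop date can come from a dedicated treatment-discontinuation eCRF page, so the programmed table might be right anyway. This part stands: the undercount is a risk created by the wording, not an established result. It does not remove the point, because a programmer who follows the only written definition would produce the wrong count.

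Some of the information also appears elsewhere. Adverse events leading to permanent discontinuation of treatment or withdrawal are in Table 2.43 and Listing 20, and Listing 2 gives subject-level reasons for stopping treatment. For reasons other than adverse events, however, no other summary table shows them by arm.

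A reader might go further in four ways that the documents do not support:

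- **That the primary estimate is affected.** Step 4 shows that no growth analysis uses this definition.
- **That Tables 1.35 and 1.36 undercount.** SAP 7.1.4 has its own wording, which asks that the child continue in the study, not that every visit be completed. The child who stops at Week 20 and leaves at Week 30 meets it.
- **That off-treatment time is understated.** SAP 11.6.2 derives post-treatment time in the study from dates, and Table 1.32 summarises exposure and study duration. For the same stop time, children who stop and then leave also contribute less off-treatment follow-up than those who stop and complete.
- **That the undercount is worst in the arm that loses more children.** That depends on how many in each arm stop first and leave later, which the documents do not give.

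**Conclusion.** Wrong as written, limited to descriptive disposition reporting. Taken literally, SAP 11.6.2 removes from Tables 1.10 and 1.11 the children who stop double-blind treatment early and later leave the study or miss follow-up. It also conflicts with the stop-date rules in the same section.

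The size is unknown. The range of about 34 down to 11 counted out of 45 rests on two assumptions: that 45 of 450 stop, and that 25% to 75% of those later leave. The second has no source in the documents. If none leave and none miss follow-up, nothing is lost.

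The primary and on-treatment growth estimates stand as planned. No effect on Tables 1.35 and 1.36 is established, though the SAP should say which definition they use.

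**What to change.** In SAP 11.6.2, delete the condition that all visits, including follow-up, were completed. Define treatment discontinuation as permanent stop of double-blind treatment before the end of the treatment period in a randomised participant, regardless of later study status.

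Apply this one definition to Tables 1.10 and 1.11 and to the Kaplan-Meier plot, and state that the intercurrent-event summaries (Tables 1.35 and 1.36) use it too. If the subgroup who stopped treatment but completed the study is of interest, show it by cross-classifying discontinuation against study completion.

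The cost is one deleted clause and a cross-reference. The stop date is already in the eCRF, so no new data are needed, and no growth analysis changes.
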